9.1. Study design

This study will be a UK-wide, multi-centre, non-interventional cohort study (Figure 1). The study will involve secondary use of hospital medical records (paper-based or electronic, as

appropriate), collected both retrospectively and prospectively, from patients' medical records. Data will be collected for a maximum of 3 years following enrollment into the IPP.

[figure not shown]
Consent from living patients will be required if data are collected by pH Associates. In that case, patients will be provided with information about the study and approached for consent by members of the direct care team, either by post or in person at a routine hospital visit. Since no consent can be obtained if the patient is deceased, identifiable medical records of deceased patients will be accessed for study data collection by the direct care team only, to preserve confidentiality and avoid bias arising from exclusion of deceased patients.

Data will be collected retrospectively from the point of patient's enrollment into the IPP until initial data collection, expected to take place between November 2018 and February 2019. Members of the direct care team, or researchers from pH Associates (for living patients only), will collect existing (retrospective) data from the medical records of eligible patients in an electronic case report form (eCRF).

After the initial retrospective data collection, data will be collected prospectively up to a maximum of 3 years from enrollment in the IPP by members of the direct care team by updating the eCRF with any subsequent therapeutic and progression data available in the medical records until the end of the 3 year follow-up period.

The palbociclib initiation date will be defined as the index date. The baseline period will extend from the date of diagnosis up to palbociclib initiation (index date). The post-initiation observation period will be defined as the period from the index date until the end of the 3 year follow-up period. Patients will contribute data up to the time that they are lost to follow-up (for example due to discharge, death or other reasons) or 3-year post-index observation period, whichever is sooner.

Figure 1. Schematic of study design

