The following definitions will be implemented. PFS will be defined as the time from the date of palbociclib initiation to the date of first documented disease progression (i.e. mention of disease progression or mixed response in the medical records, e.g. due to evidence of a new site of disease, or increasing disease, after treatment initiation) or death. OS will be defined as the time from the date of palbociclib initiation until death from any cause. Time to achieving best overall response will be defined in patients who respond to treatment as the time from the date of palbociclib initiation until achievement of the best overall response: CR, or PR if CR is not achieved during follow-up. Duration of response will be defined as the time from the date CR or PR was first documented (whichever is recorded first) to the date of first documented disease progression or death from any cause (whichever occurs first).

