9.5. Study size

This is a descriptive study and there is no *a priori* hypothesis specified. Therefore the sample size has been chosen pragmatically, based on the available patients from the IPP.

Across the entire UK, 846 women received palbociclib as part of the IPP. In the sites selected for this study, approximately 250 patients (exact number will be updated after site confirmation and patient consent) received palbociclib as part of the IPP. All eligible patients within the selected sites will be recruited into the study.

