Definitions will be implemented as described in section 9.3 Variables. Patients who are known to be alive at the date of data collection (1-year for interim report and 3-year for full study report) will be censored at the date of data collection, and patients who are lost to follow-up will be censored on the date they were last known to be alive (e.g. date of last recorded hospital visit). Patients who are alive and free from disease progression at the date of data collection and those lost to follow-up will be censored on the date they were last known not to have disease progression (i.e. the date of last documented response assessment). Patients remaining in CR or PR at the end of the post-initiation observation period or lost to follow-up will be censored on the date CR or PR was last documented.

For the estimation of the proportion of patients alive, and free from disease progression, the denominator will be all patients known to be alive at the selected time-points (1 years, 2 years and 3 years). For the estimation of the proportion of patients achieving PR, CR and with stable disease at the selected time-points (1 years, 2 years and 3 years), the denominator will be all patients with at least one assessment of response (CR / PR / no response or stable disease / progressive disease) in the past year. Estimation of time to achieving best overall response and duration of response; and representation using swimmer plots will be performed in patients who respond (achieve CR or PR during follow-up) only.

Median PFS, OS, time to achieving best overall response, time to palbociclib dose modification and time to palbociclib discontinuation, and corresponding 95% CIs, will be estimated using Kaplan-Meier curves. Assessments of response (CR / PR / no response or stable disease / progressive disease) in patients responding to treatment (achieving CR or PR following initiation of palbociclib) will be represented using “swimmer plots”.

All percentages will be reported to the nearest whole number; therefore, in reporting study results in tables, figures and associated text, percentages may not add up to 100% due to rounding.

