4 HYPOTHESES AND DECISION RULES

4.1 STATISTICAL HYPOTHESES

This is a descriptive study and there is no a priori hypothesis specified.

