Secondary Objective 2: To describe overall survival and progression-free survival, response (CR, PR), stable disease. This includes estimating the proportion of patients achieving those endpoints at 1, 2 and 3 years following palbociclib initiation; median survival, time to response and duration of response. In patients who respond to treatment, to describe PR and CR using "swimmer plots".

- Proportion of patients at 2-years following initiation of palbociclib who:
 - Are free from disease progression.
 - Are alive
 - Achieved PR
 - Achieved CR
 - Had stable disease
- Median (95% confidence interval [CI]):
 - PFS

PFIZER CONFIDENTIAL

- OS
 - Time to achieving best overall response
- Length of follow-up
- Best response to palbociclib, overall and by de novo and relapse status
- Time to best response – by de novo and relapse status
- Time to first response – overall and by de novo and relapse status

Secondary Objective 3: To describe the occurrence of neutropenia during the first-year post-initiation observation period.

- In the 6 months post-palbociclib initiation, proportion of patients who experience,
 - Neutropenia (overall and by grade, recorded and inferred from ANC measurements).
 - Worst neutropenia experienced within 3 months of palbo initiation
 - Febrile Neutropenia.

[figure not shown]
Secondary Objective 4: To describe the occurrence of gastro-intestinal toxicity, including diarrhoea, nausea and vomiting during the first-year post-initiation observation period.

- For each cycle, proportion of patients who experience Gastro-intestinal toxicity, including:
 - Diarrhoea.
 - Severity
 - Nausea.
 - Severity
 - Vomiting.
 - Severity
- Proportion of patients experiencing an AE during follow-up

Secondary Objective 5: To describe progression of clinical indicators, including biochemical and radiological indicators at each time-point available during the first year following palbociclib treatment initiation.

- Summary measures of full blood counts in the first 6 months following initiation:
 - Haemoglobin.
 - White cell counts.
 - Absolute neutrophil counts.
 - Platelet counts.
- Summary measures of liver function tests in the first 6 months following initiation:
 - aspartate transaminase (also called aspartate aminotransferase).
 - alanine transaminase (also called alanine aminotransferase).
 - alkaline phosphatase.
 - Albumin
 - Bilirubin

PFIZER CONFIDENTIAL

[figure not shown]

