prescribed treatment in the 1st, 2nd, and 3rd line after palbociclib discontinuation was presented as a categoric variable as per section 8.1.2. Dose, duration of subsequent treatments and number of completed 28-day cycles per patient were presented as quantitative variables as per section 8.1.1. Number of completed 28-day cycles (categories: 1-6 cycles, 7-12 cycles, 13-18 cycles, 19-24 cycles, 25-27 cycles and No completed cycles) and the proportion of patients co-administered letrozole or fulvestrant were presented as categoric variables as per section 8.1.2. All other endpoints were evaluated as proposed.

8.2.3 Secondary Objective 2: To describe overall survival and progression-free survival, response (CR, PR), stable disease. This includes estimating the proportion of patients achieving those endpoints at 1 and 2 following palbociclib initiation: median survival, time to response and duration of response. In patients who respond to treatment, to describe PR and CR using “swimmer plots”.

Proposed: For the estimation of the proportion of patients alive, and free from disease progression, the denominator will be all patients known to be alive at the selected time-points (e.g., 1 years, 2 years, and 3 years). For the estimation of the proportion of patients achieving PR, CR and with stable disease at the selected time-points (1 years and 2 years), the denominator will be all patients with at least one assessment of response (CR / PR / no response or stable disease / progressive disease) in the past year.

[figure not shown]
Actual: Proportion of patients free from disease progression, are alive, achieved PR, CR or stable disease were analysed separately at the 2-year timepoint only. Length of follow-up, and time to best response and first response were presented as quantitative variables as per section 8.1.1. Best response to palbociclib, overall and by de novo and relapse status was treated as a categoric variable and analysed according to section 8.1.2.

8.2.4 Secondary Objective 3: To describe the occurrence of neutropenia during the first-year post-initiation observation period.

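### Response is counted over the whole follow-up, so a CR or PR on a later treatment line can be reported as best response to palbociclib

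*Protocol*

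**What the plan says.** Protocol 9.7 confines the estimation of time to best overall response and duration of response, and the swimmer plots, to "patients who respond (achieve CR or PR during follow-up) only". The same section explains responding to treatment as reaching CR or PR after palbociclib was started, with no closing date. Protocol 9.3 sets best overall response as "CR, or PR if CR is not achieved during follow-up", and SAP section 6 repeats that definition. The duration-of-response row in SAP 8.2.9 uses the same window.

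The window is long. Protocol 9.1 states: "The post-initiation observation period will be defined as the period from the index date until the end of the 3 year follow-up period". A patient leaves it earlier only through loss to follow-up or death. Protocol 9.3 collects response assessments over all of follow-up, and up to three lines of medication after palbociclib within it. The SAP shortens the analysis to two years (5.1 and 8.1) but does not tie it to treatment.

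The SAP names the endpoint in section 6 as "Best response to palbociclib, overall and by de novo and relapse status". The account of completed analyses in 8.2.3 says "Best response to palbociclib, overall and by de novo and relapse status was treated as a categoric variable".

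Duration of response runs from the first recorded CR or PR to the first recorded progression or death (Protocol 9.3, SAP 6). The only response-specific censoring date is the last documented CR or PR (Protocol 9.7, SAP 8.2).

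**The concern.** Neither document ends the response window at progression, at palbociclib discontinuation or at the start of another anticancer drug. A patient whose best result on palbociclib is stable disease, who progresses and then has a PR on the next therapy, meets the definition of a responder. A patient with a PR on palbociclib and a CR on the next line has a best response of CR. Both would be tabulated under a heading that credits palbociclib.

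The affected results are best overall response, time to first and best response, and the choice of patients for the swimmer plots. Late responses also tend to lengthen time to best response. A reader of the final report could not separate the effect of palbociclib from that of its successors. The planned checks may not catch this: Protocol 9.8 provides independent review of the primary endpoint analysis only.

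**Working it through.** **No stated figure to reproduce.** Protocol 9.5 says "the sample size has been chosen pragmatically, based on the available patients from the IPP", and neither document gives an expected response rate. The defect follows from the definitions; the arithmetic only illustrates its size.

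**Definitions applied to one patient.** Suppose progression on palbociclib at month 12, a new therapy, and a first PR at month 17.
- PFS is 12 months.
- The patient is a responder, with time to best response of 17 months, later than the PFS event.
- Duration of response, read literally, is 12 − 17 = −5 months. If the end point is read as the first progression after the response, the duration is positive but describes the next therapy.

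**Direction.** Best overall response is the best result over a set of assessments. Adding later assessments can leave it unchanged or improve it, never worsen it. The proportions at fixed time-points differ: Protocol 9.7 takes as denominator all patients with a response assessment in the past year. Next-line scans showing stable or progressive disease enter that denominator too, so the CR or PR proportion may move either way.

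**Illustrative size: inputs**
- Median PFS 20.2 and 24.8 months: the first-line palbociclib arms cited in Protocol section 7.
- N = 200: SAP 2.1 (Protocol 9.5 has about 250; percentage points do not depend on N).
- Horizon T = 24 months (SAP) or 36 months (protocol).
- Assumed, not in the documents: response on palbociclib p = 30–55%; next-line response r = 5–30%; at least 4 months of follow-up left after progression; exponential PFS, the same for non-responders as for all patients.

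**Step 1.** PFS event by T = 1 − exp(−ln 2 × T / median). At 24 months this is 0.489 (median 24.8) and 0.561 (median 20.2); at 36 months, 0.634 and 0.709.

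**Step 2.** With 4 months left, q = 1 − exp(−ln 2 × (T − 4) / median). At 24 months this is 0.428 and 0.497; at 36 months, 0.591 and 0.666.

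**Step 3.** The rate as written is p + (1 − p) × q × r. The rate limited to palbociclib is p. The excess is (1 − p) × q × r.

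| T | Case | (1 − p) × q × r | Points added | Patients of 200 |
|---|---|---|---|---|
| 24 | lowest | 0.45 × 0.428 × 0.05 | 1.0 | 1.9 |
| 24 | mid | 0.60 × 0.428 × 0.10 | 2.6 | 5.1 |
| 24 | highest | 0.70 × 0.497 × 0.30 | 10.4 | 20.9 |
| 36 | lowest | 0.45 × 0.591 × 0.05 | 1.3 | 2.7 |
| 36 | mid | 0.60 × 0.591 × 0.10 | 3.5 | 7.1 |
| 36 | highest | 0.70 × 0.666 × 0.30 | 14.0 | 28.0 |

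In the 2-year mid case, 40.0% becomes 42.6%.

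**Limits of the illustration.** PFS events include deaths, and the dead cannot respond later, so q is somewhat high. Non-responders probably progress sooner than average, which works the other way. The cohort includes a second-line group (SAP 5.4), to which first-line medians need not apply. Upgrades from PR to CR are not counted, because they change the category and not the number of responders.

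**The case against.** The strongest reply is that an on-treatment meaning is plain from the labels: Protocol 9.3 speaks of patients who respond to treatment, and the SAP names palbociclib. On that view the window is merely under-specified, and the eCRF or data collection guidelines, which are not available here, may close it. The labels do suggest that intent, but no rule in either document carries it out, and Protocol 9.7 explains responding as CR or PR after initiation. Where the SAP wants an on-treatment limit it writes one: section 6 defines concomitant medications as those given while on palbociclib. A programmer following the text would count next-line responses.

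Other parts of the reply stand, and they rule out stronger readings that a reader might draw.
- **Impossible durations as a certainty.** The negative value needs the literal reading of first progression, and the duration row in SAP 8.2.9 omits the word first. Duration of response is also absent from the Objective 2 endpoint list in SAP 6, which is meant to reflect the analyses conducted, and from the completed-analysis text in 8.2.3. It may not have been produced.
- **Every response proportion overstated.** This is certain in direction only for best overall response.
- **A known size.** The next-line and on-palbociclib response rates are assumptions.
- **A threat to the study's main result.** SAP 4.1 says "This is a descriptive study and there is no a priori hypothesis specified". The primary objective is baseline description, and PFS and OS do not use the response window. Swimmer plots show progressive disease too, so a response after progression would be visible there.

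**Conclusion.** The point holds as a mismatch between definition and label. As written, the response endpoints cover all treatment received during follow-up, while the SAP reports them as response to palbociclib. Best overall response can only be raised by this; the effect on the 1-, 2- and 3-year CR, PR and stable-disease proportions has no certain direction (the SAP's completed-analysis text reports these at 2 years only). Duration of response, if produced, would be negative or would describe the next therapy for patients whose first response follows progression.

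The plausible size at 2 years is about 1 to 10 percentage points, or about 2 to 21 of 200 patients, with a mid case near 2.6 points. That range depends on the assumed response rates, exponential PFS at the cited first-line medians and the 4-month allowance; it is not an estimate from the study. This should be fixed, but it is not critical, because response is part of a secondary objective in a descriptive study.

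**What to change.** In Protocol 9.3 and 9.7 and SAP 6, 8.2.3 and 8.2.9:
- Define response, best overall response, time to first and best response, and the swimmer-plot population from assessments after the index date, up to the earliest of first documented progression, palbociclib discontinuation (with a stated assessment window), start of a new anticancer therapy, or end of follow-up.
- End duration of response at the first progression or death after the response, and censor it at the start of new therapy.
- List later responses separately by line of therapy.

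The dates needed (progression, palbociclib stop, subsequent lines) are in, or can be derived from, the planned dataset, so no new data items should be required; start dates for later lines should be confirmed in the eCRF. Protocol 9.7 lets the SAP modify the planned analyses and calls for a protocol amendment only for major changes to the primary endpoint, so the SAP can carry the change first. The cost is real but modest: SAP 8.2.3 describes analyses already run, so the response tables and plots would have to be rerun, and the reported response proportion would probably be slightly lower.

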9.8. Quality control

All data collectors will be provided with Data Collection Guidelines to facilitate consistent completion of the eCRF and will receive training in the requirements of the study protocol and correct completion of the eCRF prior to commencement of data collection.

The accuracy and quality of data collection will be monitored by reference to source data (source data verification [SDV]).

SDV will be performed on the complete dataset of a random sample of at least 10% of patients from each centre. Any issues identified by pH Associates relating to quality, accuracy or consistency of data collection will be discussed with the data collector concerned and further training provided by pH Associates if required. If any subsequent issues are identified related to quality, accuracy or consistency of data collection, a random check of a further 10% of data collected by that data collector will be undertaken. Should any further issues be identified, 100% SDV will be undertaken at the centre. It is the centre Investigator's responsibility to ensure the accuracy of the data entered in the CRFs.

Where patient study data are collected by pH Associates, SDV will be performed by a pH Associates study monitor who did not collect data for that patient record. For patients whose entire dataset was collected by members of patients' direct care team, a 'back-to-back' SDV will be performed with a member of the direct care team, as these patients will not have provided consent to their data being accessed by external researchers from pH Associates. This will involve the direct care team member at the centre reciting data from the patient notes to the pH Associates study monitor so that they can verify the data in the eCRF without the need to look directly at the identifiable source records.. All people performing SDV will be trained by pH Associates.

All clinical data submitted will be checked for eligibility, completeness and accuracy by the pH Associates data management team using agreed manual and programmed validation checks and queries will be raised. Study centres will be required to co-operate with the data management team in the resolution of these queries.

Analysis of the primary endpoint will be independently reviewed by a member of the Data Analysis team at pH Associates who was not involved in the analysis of the final study data. No additional analysis checks will be carried out.

Investigators taking part in the study will have all required training for delivery of the study

9.9. Limitations of the research methods

- Comparisons of the results of this study with that of clinical trials and other real-world studies may be limited due to the presence of several potential sources of bias.
- Several sources of selection bias may be introduced in the study:

- At sites where data are collected by pH Associates, consent from living patients will be required; and consequently a low rate of consent amongst living patients may introduce an over-representation of deceased patients (for whom consent is not required) at those sites, and also compared to sites where consent is not required as all data are collected by the direct medical care team.
- Patients were treated as part of routine care and therefore patients enrolled in this study may have more diverse characteristics than in a clinical trial setting (for example with regard to menopausal status, ER and PR status, HER2 status), which may impact on the efficacy of palbociclib.
- Patients will be recruited from larger centres enrolled in the IPP, which may differ from smaller centres in terms of demographic and clinical characteristics, and therefore may not be representative of all patients treated with palbociclib in routine care as part of the IPP.
- Patients may be lost to follow-up due to the occurrence of AEs, lack of efficacy or other reasons, introducing attrition bias. However, the use of Kaplan-Meier curves will be used to obtain estimates of median PFS OS, CR, PR and this takes into account patient attrition.
- Radiological results will be collected from medical notes recorded by radiologists who were unblended to patient's treatment, introducing potential measurement bias.
- The interpretation of data collected retrospectively will be dependent on the completeness and quality of the medical records and the reliability of the abstraction of data from the medical records. However, SDV will be employed to identify and correct abstraction errors.
- This is a descriptive study and no analyses to control for confounding will be carried out; therefore, no definitive causal relationships between Ibrance® and study endpoints can be made.
- At sites where data are collected by pH Associates, a low consent rate may diminish sample size and the target of 250 patients enrolled into the study may not be achieved. If <200 patients are recruited into the study, an expansion of the study to other sites involved in the IPP will be considered.

